## Appendix 1 Schedule of Assessments and Procedures (cont.)

- Start of second cycle after cross over, Day 1  $\pm$  1 week
  - On Day 1 of Cycles 5, 8, and 11 after cross over (every three treatment cycles)  $\pm$  2 weeks
  - On Day 1 of Cycles 15, 19, and 23 after cross over (every four treatment cycles)  $\pm$  2 weeks
  - On Day 1 of Cycles 29, 35, 41, 47 after cross over, etc. (every six treatment cycles)  $\pm$  2 weeks
  - End-of-study-treatment visit
7. Hematology includes hemoglobin, hematocrit, WBC with differential (neutrophils, lymphocyte, monocyte, eosinophil and basophil counts, and other cells), and platelet count. Screening hematology values must be obtained within 14 days of Cycle 1 Day 1. Note: If screening laboratory specimens are collected within 7 days of the Cycle 1, Day 1 visit, they do not have to be repeated at Day 1.
  8. Chemistry includes BUN, creatinine, sodium, potassium, chloride, bicarbonate, phosphorus, magnesium, total calcium, albumin, LDH, and CPK. LFTs include ALT, AST, total bilirubin, ALP, and GGT. Screening chemistry values must be obtained within 14 days of Cycle 1 Day 1. Note: If screening laboratory specimens are collected within 7 days of the Cycle 1, Day 1 visit, they do not have to be repeated at Day 1.
  9. For women of childbearing potential, a serum pregnancy test is required at screening within 14 days prior to Cycle 1 Day 1. Women who have had amenorrhea for  $>$  12 months but  $<$  2 years should have an FSH test at screening for eligibility purposes.
  10. This is performed only during screening. Both blood glucose and lipid panel must be obtained after at least an 8-hour fast. Lipid panel should include total cholesterol, low-density lipoprotein and triglycerides.
  11. All patients must have a screening brain CT or MRI to assess for brain metastasis, and subsequently only as clinically indicated.
  12. The frequency, method, and evaluation criteria for tumor assessments will be determined by the investigator per local clinical practice. Response may be assessed using RECIST v1.1. Assessments should include CT scans of the chest, abdomen and pelvis, with an evaluation of all known or suspected sites of disease, whenever possible. The same radiographic procedure used at screening should be used throughout the study.
  13. PK sample for analysis of vemurafenib concentration will be collected in sodium heparin tubes and will require 2mL of venous blood at each timepoint. PK sample for analysis of cobimetinib concentration will be collected in K2-EDTA tubes and will require 3mL of venous blood at each timepoint. The time and date of all PK samples must be documented. Plasma samples for vemurafenib and cobimetinib concentration measurement will be collected at the following time-points:
    - 1–4 hours after the first dose on Cycle 1, Day 1
    - Pre-dose on Cycle 1, Day 15  $\pm$  3 days
    - 2–4 hours post-dose on Cycle 1, Day 15  $\pm$  3 days
    - Pre-dose on Cycle 2, Day 15  $\pm$  3 days
  14. For both investigational drugs, dosing will continue until disease progression, consent withdrawal, or unacceptable toxicity. Dispense a sufficient number of vemurafenib and cobimetinib to last until the next visit. Extra medications may be dispensed if there is a reasonable possibility that the patient's next visit may be delayed (e.g., because of inclement weather or distance of patient's home from study center).

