### **3.3.2 Rationale for Patient Population**

The proposed study will enroll treatment-naïve patients with unresectable locally advanced Stage IIIc or metastatic melanoma as defined by the American Joint Committee on Cancer (AJCC) classification v.7. This study will be conducted only in patients whose melanoma harbors the BRAF V600 mutation. This represents the population for which vemurafenib is indicated. The cobas® 4800 BRAF V600 mutation test is the approved companion diagnostic test for vemurafenib and will be used to determine the presence of the BRAF V600 mutation.

Several exclusion criteria were put in place to ensure patient safety going into the study. Patients who are pregnant are not allowed on the study as the effect of vemurafenib and cobimetinib on the developing fetus is not known. Similarly, patients and their partners are required to use of effective contraception.

Given that vemurafenib results in mild QTc prolongation, patients will be required to have a baseline screening ECG and those whose QTc interval is >450 ms or who have congenital long QT syndrome will be excluded.

To mitigate the risk of ophthalmologic adverse events associated with MEKi as a class effect, patients are required to undergo ophthalmologic examination to evaluate risk factor for or findings indicative of neurosensory retinal detachment, CSCR or retinal vein occlusion (RVO) prior to starting study treatment. Patients with such conditions will be excluded.

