##### General Inclusion Criteria:

8. Male or female patient aged  $\geq 18$  years.
9. Able to participate and willing to give written informed consent prior to performance of any study-related procedures and to comply with the study protocol.
10. Life expectancy  $\geq 12$  weeks.
11. Adequate hematologic and end organ function, defined by the following laboratory results obtained within 14 days prior to first dose of study drug treatment:
  - ANC  $\geq 1.5 \times 10^9/L$
  - Platelet count  $\geq 100 \times 10^9/L$

- Hemoglobin  $\geq 9$  g/dL
  - Albumin  $\geq 2.5$  g/dL
  - Bilirubin  $\leq 1.5 \times$  the upper limit of normal (ULN)
  - AST, ALT, and ALP  $\leq 3 \times$  ULN, with the following exceptions:
    - Patients with documented liver metastases: AST and/or ALT  $\leq 5 \times$  ULN
    - Patients with documented liver or bone metastases: ALP  $\leq 5 \times$  ULN
  - Serum creatinine  $\leq 1.5 \times$  ULN or CrCl  $\geq 40$  mL/min on the basis of measured CrCl from a 24-hour urine collection or Cockcroft-Gault glomerular filtration rate estimation:  

$$\frac{(140 - \text{age}) \times (\text{weight in kg}) \times (0.85 \text{ if female})}{72 \times (\text{serum creatinine in mg/dL})}$$
12. Female patients of childbearing potential and male patients with partners of childbearing potential must agree to always use 2 effective forms of contraception during the course of this study and for at least 6 months after completion of study therapy.
- Females of childbearing potential are defined as sexually mature women without prior oophorectomy or hysterectomy who have had menses within the last 12 months.
  - Females are not considered to be of childbearing potential if amenorrheic for  $> 12$  months and follicle-stimulating hormone (FSH) level  $\geq 40$  IU/L.
  - For females who have been amenorrheic for  $\geq 2$  years, the requirement for FSH measurement at screening will be waived.
  - Effective forms of contraception includes surgical sterilization, a reliable barrier method with spermicide, birth control pills, or contraceptive hormone implants. Please note that potential interactions between vemurafenib and hormonal contraceptives may decrease the effectiveness of hormonal contraceptives.
  - Male patients who are surgically sterilized are required to use barrier methods of contraception.
13. Negative serum pregnancy test within 14 days prior to commencement of dosing in women of childbearing potential.

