#### **4.5.1.8 Laboratory Assessments**

All screening laboratory assessments should be obtained within 14 days prior to initiation of study drug on Cycle 1, Day 1. Note: If screening laboratory specimens are collected within 7 days of the Cycle 1, Day 1 visit, they do not have to be repeated at Day 1.

Laboratory assessments required on the study are as follows:

Hematology:	Hemoglobin, hematocrit, WBC count with differential (neutrophils, lymphocyte, monocyte, eosinophil and basophil counts, and other cells), and platelet count.
Chemistry:	BUN, creatinine, sodium, potassium, chloride, bicarbonate, phosphorus, magnesium, total calcium, albumin, LDH, CPK, fasting blood glucose, and fasting lipid panel.
Liver function tests:	ALT, AST, total bilirubin, ALP, and GGT.
Pregnancy test and FSH:	All women of childbearing potential (as defined in inclusion criteria) will have a serum pregnancy test at screening. Women who have had amenorrhea for > 12 months but < 2 years should have a screening FSH.

These laboratory assessments will be analyzed at the study site's local laboratory.

Blood and tumor tissue samples for biomarker, pharmacogenomics sample, and PK samples will be sent to one or several Roche-designated central laboratories or to the

Sponsor for analysis. Instruction manuals and supply kits will be provided for all central laboratory assessments.

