### ***Teratogenicity and Development Toxicity***

In a dedicated nonclinical embryo-fetal toxicity study, cobimetinib produced fetal toxicity (resorptions and reductions in fetal weight), and teratogenicity (malformations of the great vessels and skull) at similar systemic exposures in rat to those observed in patients administered the 60 mg dose.

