#### **5.4.3 Reporting Requirements for Pregnancies**

##### **5.4.3.1 Pregnancies in Female Patients**

Female patients of childbearing potential will be instructed to immediately inform the investigator if they become pregnant during study treatment or within 6 months after the last dose of study drug. All women of childbearing potential will have a serum pregnancy test at screening.

A Pregnancy Report eCRF should be completed by the investigator immediately (i.e., no more than 24 hours after learning of the pregnancy) and submitted via the EDC system. A pregnancy report will automatically be generated and sent to Roche Safety Risk Management. Pregnancy should not be recorded on the Adverse Event eCRF. The investigator should discontinue study drug and counsel the patient, discussing the risks of the pregnancy and the possible effects on the fetus. Monitoring of the patient should continue until conclusion of the pregnancy.

In the event that the EDC system is unavailable, a Pregnancy Report worksheet and Pregnancy Fax Coversheet should be completed and faxed to Roche Safety Risk Management or its designee within 24 hours after learning of the pregnancy, using the fax numbers provided to investigators (see "Protocol Administrative and Contact Information and List of Investigators").

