  - On Day 1 of Cycles 5, 8, and 11 (every 3 treatment cycles)  $\pm$  2 weeks
  - On Day 1 of Cycles 15, 19, 23 (every 4 treatment cycles)  $\pm$  2 weeks
  - On Day 1 of Cycles 29, 35, 41, 47 etc. (every 6 treatment cycles)  $\pm$  2 weeks
  - End-of-study-treatment visit

Evaluation of left ventricular function does not need to be performed at end-of-study-treatment visit if it has been performed within the last 12 weeks. Any patient who develops clinical signs or symptoms suspicious of cardiac failure should undergo an LVEF assessment. Evaluation of left ventricular function must be performed by the same method for each patient.

For patients who cross over from placebo to cobimetinib treatment, the ECHO/MUGA schedule must begin again, with exams at the following timepoints:

- Within 28 days of, but not after the first day of cross over

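### Control-arm women who cross over to cobimetinib need no pregnancy test before their first cobimetinib dose

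*Protocol*

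**What the plan says.** Every pregnancy-test provision in the protocol is attached to original screening.

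- Section 4.1.1, inclusion criterion 13: "Negative serum pregnancy test within 14 days prior to commencement of dosing in women of childbearing potential".
- Section 4.5.1.8: "All women of childbearing potential (as defined in inclusion criteria) will have a serum pregnancy test at screening".
- Section 5.4.3.1: "All women of childbearing potential will have a serum pregnancy test at screening".
- Appendix 1, footnote 9: "For women of childbearing potential, a serum pregnancy test is required at screening within 14 days prior to Cycle 1 Day 1". The matching row of the schedule is marked only in the screening column.
- Section 4.5.2.1 lists the test among the screening assessments. Section 4.5.2.2, the list of assessments during the study, has none.

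Control-arm patients may cross over to vemurafenib plus cobimetinib (Sections 3.1 and 3.3.3; Appendix 1, footnote 2). The conditions are that they are still on vemurafenib, have not progressed, give consent, stay in survival follow-up, and that the investigator expects benefit. For these patients the ECHO/MUGA schedule (Section 4.5.1.11; Appendix 1, footnote 6) and the ophthalmologic schedule (Section 4.5.1.7; Appendix 1, footnote 20) start again. In each, the first examination is timed "Within 28 days of, but not after the first day of cross over".

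On fetal risk, Section 5.1.2.2 reports fetal toxicity and malformations with cobimetinib "at similar systemic exposures in rat to those observed in patients administered the 60 mg dose". Section 3.3.2 excludes pregnant patients because "the effect of vemurafenib and cobimetinib on the developing fetus is not known".

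**The concern.** The protocol treats crossover as a new start of cobimetinib for eye and cardiac safety, but not for pregnancy, which can also change after screening. Women randomized to cobimetinib had a negative test within 14 days before their first dose. Women who reach the same first dose by crossover need no current test.

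At stake is exposure of an unrecognized pregnancy to a drug with rat teratogenicity at clinically relevant exposure. Two contraceptive methods are still required, but criterion 12 itself warns that "potential interactions between vemurafenib and hormonal contraceptives may decrease the effectiveness of hormonal contraceptives", and crossover patients are by definition still taking vemurafenib. The point concerns participant safety and has no bearing on the PFS or OS comparison.

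**Working it through.** The protocol gives no figure to reproduce. The check has two parts: whether any provision supplies the missing test, and how old the last required test would be.

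**1. Is a test required before crossover?**

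| Item | Before Cycle 1 Day 1 | Before first cobimetinib dose at crossover |
|---|---|---|
| Ophthalmologic examination | Required | Listed, within 28 days |
| ECHO/MUGA | Required | Required, within 28 days |
| Serum pregnancy test, women of childbearing potential | Required, within 14 days | Not mentioned |

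Criterion 13 speaks of the start of dosing, but it is a study-entry criterion, and footnote 9 ties the test to Cycle 1 Day 1. It cannot reasonably be read as applying again at crossover.

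**2. How old is the last required test at crossover?**

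Section 4.2 keeps the study blinded until the final OS analysis is complete and releases treatment assignments to sites only after that. The final OS cutoff is therefore an early bound for the crossover date.

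*From reported dates (Section 1.4.4).* At the 9 May 2014 cutoff 247 + 248 = 495 patients were enrolled, so every screening test had been done by then. The final OS cutoff was 28 August 2015.

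- 9 May 2014 to 9 May 2015: 365 days
- 9 May to 28 August 2015: 22 + 30 + 31 + 28 = 111 days
- Minimum age: 365 + 111 = 476 days; 476 / 30.44 = 15.6 months
- Relative to the entry window: 476 / 14 = 34 times

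*From the planned timeline.* The final OS cutoff is projected at 31 months after the first patient (Table 12). Enrollment lasts about 14 months (synopsis, Length of Study) or 12.7 months (Table 12).

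- Last patient enrolled: 31 − 14 = 17 months, or 31 − 12.7 = 18.3 months
- First patient enrolled: about 31 months

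**3. How many patients could be affected?**

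The protocol does not say. A rough upper guide for control patients still progression-free assumes exponential PFS with the reported control median of 6.2 months and 248 patients (Section 1.4.4).

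- At 15.6 months: 0.5^(15.6/6.2) ≈ 0.17; 0.17 × 248 ≈ 43
- At 31 months: 0.5^(31/6.2) = 0.5^5 ≈ 0.03; 0.031 × 248 ≈ 8

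These counts include men and women not of childbearing potential, and ignore patients who stopped vemurafenib for toxicity. The number of women concerned would be smaller still.

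**The case against.** The strongest reply is that the protocol has one uniform rule: a single test at screening, then two contraceptive methods, immediate reporting and mandatory discontinuation if pregnancy occurs (Sections 4.1.1, 5.4.3.1 and 4.6.1.1). No sentence contradicts another. A woman in Arm B resumes cobimetinib every cycle after seven days off, without retesting, so late in treatment she is in much the same position as a woman crossing over. The eye and cardiac schedules restart because they monitor change from a baseline. Entry tests in general are not repeated: fasting glucose and lipids are also done only at screening. The group is small, the teratogenicity evidence is nonclinical and listed under potential risks, and the age of a test is not itself a measure of risk.

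Much of this is fair. It is a gap and not a contradiction, the absence of on-treatment retesting in both arms is a wider choice that this point does not challenge, and the numbers are probably low. The ECHO/MUGA restart is also worded more firmly than the eye restart, although both list an examination before crossover.

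What does not stand is that the existing safeguards replace a test. Contraception reduces the chance of pregnancy. Reporting and discontinuation act only after a pregnancy is recognized. Criterion 13 requires a test at entry even though criterion 12 already requires contraception, so the protocol itself does not regard contraception as sufficient before first exposure. Crossover is also first exposure to cobimetinib.

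**Conclusion.** The concern holds. Followed as written, the protocol lets a woman of childbearing potential take her first cobimetinib dose on a pregnancy test at least 476 days old on the reported dates, or about 17 to 31 months old on the planned timeline. The cobimetinib arm had a maximum of 14 days. The 476-day floor assumes that crossover follows the final OS analysis, as Section 4.2 provides, and that no site tests on its own initiative. The number of women affected is unknown and may be small. The change should be made because the possible harm is serious and the remedy is simple. No efficacy result depends on it.

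**What to change.** Add to Appendix 1, footnote 9, and to Section 4.5.2.2: for women of childbearing potential who cross over from placebo to cobimetinib, a negative serum pregnancy test is required within 14 days before the first cobimetinib dose after crossover.

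The cost is one local-laboratory serum assay per woman concerned and the wait for its result. The sample can be taken at the pre-crossover eye or ECHO/MUGA visit if that falls within 14 days of the first dose, or with a routine chemistry draw, provided the result is available before dosing.

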## Appendix 1 Schedule of Assessments and Procedures (cont.)

15. Provide a medication diary. Instruct patient to record the time and date they take each study drug dose in the diary and to return all unused capsules at each study visit to assess compliance. Collect and review medication diary, collect unused medications, and assess compliance at each subsequent visit. At least 7 days off cobimetinib are required prior to starting a new treatment cycle.
16. Review and capture of all concomitant medications will be performed at each study visit. Concomitant medications are defined as any prescription medications, over-the-counter preparations and supplements used by a patient within 7 days prior to Cycle 1, Day 1 and continuing through the study completion visit.
17. All adverse events and serious adverse events will be collected. All adverse events or serious adverse events occurring after study discontinuation will be recorded until 28 days after the last dose of study treatment or until initiation of another subsequent anti-cancer therapy, whichever occurs first. Any second non-cutaneous primary malignancy (related or unrelated to study treatment) that develop during or up to 12 months after study treatment completion must be reported as a serious adverse event.
18. Survival assessment will be used to collect overall survival during long-term follow-up; patient should be followed up every 12 weeks until death, withdrawal of consent, or loss to follow-up. Subsequent anti-cancer therapy information will be collected at the same time as survival assessment.
19. Dermatology evaluation: Complete evaluation of the skin by a dermatologist, or qualified equivalent medical specialist, will be conducted at baseline (up to 28 days prior to Cycle 1, Day 1), Cycle 2, Day 1 ( $\pm 1$  week), and per local standard of care thereafter while receiving study treatment and at the end-of-study-treatment visit. Dermatologic examination does not need to be performed at end-of-study-treatment visit if one has been performed within the last 12 weeks.
20. All patients will undergo ophthalmologic examination at the following timepoints:
  - Screening
  - Cycle 2, Day 1  $\pm 1$  week
  - On Day 1 of Cycles 5, 8 and 11 (every 3 treatment cycles)  $\pm 2$  weeks
  - On Day 1 of Cycles 15, 19, 23 (every 4 treatment cycles)  $\pm 2$  weeks
  - On Day 1 of Cycles 29, 35, 41, 47 etc. (every 6 treatment cycles)  $\pm 2$  weeks
  - End-of-study-treatment visit

Ophthalmologic examination does not need to be performed at end-of-study-treatment visit if one has been performed within the last 12 weeks. Baseline ophthalmologic examination evaluates for evidence of retinal pathology that is considered a risk factor for neurosensory retinal detachment, RVO, or neovascular macular degeneration. Risk factors for RVO include elevated serum cholesterol, hypertriglyceridemia, hyperglycemia, hypertension and glaucoma. Ophthalmologic examination will include visual acuity testing, intraocular pressure measurements by tonometry, slit lamp ophthalmoscopy, indirect ophthalmoscopy, and spectral domain optical coherence tomography (spectral domain OCT, if not available, may be substituted with time domain OCT).

## Appendix 1 Schedule of Assessments and Procedures (cont.)

For patients who cross over from placebo to cobimetinib treatment, the ophthalmologic examination schedule should begin again, with exams at the following timepoints:

- Within 28 days of, but not after the first day of cross over
- Start of second cycle after cross over, Day 1  $\pm$  1 week
- On Day 1 of Cycles 5, 8 and 11 after cross over (every three treatment cycles)  $\pm$  2 weeks
- On Day 1 of Cycles 15, 19, 23 after cross over (every four treatment cycles)  $\pm$  2 weeks
- On Day 1 of Cycles 29, 35, 41, 47 after cross over, etc. (every six treatment cycles)  $\pm$  2 weeks
- End-of-study-treatment visit

21. Biopsies of accessible melanoma lesions are mandatory upon patient's consent to participate in the trial. Either FFPE or fresh-frozen biopsies (or both) will be obtained at 3 timepoints:

- Baseline sample: during screening within 28 days of Cycle 1 Day 1
- On treatment cycle: on Cycle 2, Day 15 ( $\pm$  1 week)
  - Disease progression sample: at time of progressive disease

Baseline sample biopsies should be completed at least 48 hours before the initiation of study drug therapy on Cycle 1 Day 1. Archival tissue may be submitted in place of newly obtained tumor tissue for the baseline sample biopsy. It is highly recommended that the biopsy at disease progression be collected within 3 days after last study treatment. Excisional biopsies, punch biopsies, 14-gauge core needle biopsies are acceptable. Fine needle aspiration (FNA) biopsies are not acceptable.

21A. Biopsy will only be performed if patient has accessible lesion and disease progression.

22. Blood samples for biomarker analysis will be obtained on Day 1 of Cycles 1, 3, and 5, and at the time of disease progression. Blood sample required at each timepoint: one 6-mL blood sample anticoagulated in EDTA.

23. If a patient develop any cutaneous lesion(s) suspicious for SCC or KA during the study, biopsy tissue and a paired normal skin biopsy must be obtained for central pathology review. Only one normal skin biopsy is required per patient, regardless of the number of SCC lesions identified and biopsied during the study. Any suspicious lesions (cutaneous or non-cutaneous) thought to be malignant must also be sent for central pathology review and may undergo molecular characterization.

- Any second non-cutaneous primary malignancy (related or unrelated to study treatment) that develop during or up to 12 months after study treatment completion must be reported as a serious adverse event and tumor tissue sent for central pathology review.

24. Patients will undergo CT/MRI of the chest to monitor for the occurrence of SCC while on study treatment and per local standard of care.

